11.0 RISK-BENEFIT ASSESSMENT

11.1 Anticipated Risks

Refer to section 10.2 of this protocol for a detailed listing of potential risks (i.e., adverse events) of this clinical investigation. This protocol does not withhold or postpone any medically necessary treatment. If any complications are experienced, the study investigator will use good clinical judgment in the treatment of adverse events.

Based on prior literature, and preclinical and clinical studies completed, RheOx is expected to be safe for use in this clinical study.

As this is a feasibility study, unanticipated events may occur, however, every effort will be undertaken to ensure risks are minimized. The study is designed with a conservative, step-wise approach to treating each subject. Patients will be first treated in only the right airways and fully recovered for 30 days to allow for sufficient healing. The right airways will be visualized and assessed prior to further treatment on the left side. If the subject has experienced any complications that preclude continued participation in the study, then additional treatment is halted.

The study also has a planned interim analysis and stopping rules, discussed earlier, to ensure safety concerns are addressed throughout the study.

11.2 Anticipated Benefits

Gala's Chief Medical Officer, the Scientific Advisory Board (SAB) and the study Investigators have determined that this research study is justified because the overall potential benefit to the population outweighs its attendant risks. If the investigational treatment is successful, participating subjects may experience a reduction in symptoms, an improved quality of life and potentially reduced exacerbations associated with chronic bronchitis. All subjects will be symptomatic at baseline (per the study inclusion criteria), despite standard of care pharmacotherapy. Thus, additional benefit from the treatment may reduce the burden of disease on the healthcare system. Additionally, results of this study may lead to further development of a new, minimally invasive therapy, RheOx, which could lead to an alternative therapy to chronic bronchitis.

12.0 STUDY MANAGEMENT

12.1 Statement of Compliance

The study will be conducted in accordance with applicable regulations for clinical research, 21 CFR Part 812, ISO 14155, the ICH guidelines for good clinical practice and company standard operating procedures (SOPs). The study will be registered on www.clinicaltrials.gov.

12.2 Institutional Review Board (IRB)

The clinical investigational plan and site informed consent must be approved by the IRB for the given institution prior to any study-related activity. The investigator is responsible for complying with all applicable requirements established by the IRB.

The study sponsor will maintain a list of the names, addresses, and chairpersons of all IRBs that have or will be asked to review the investigation and a certification of IRB action concerning the investigation (when available).

12.3 Investigator Responsibilities

The Principal Investigator is responsible for ensuring that the clinical investigation is conducted according to the Investigator Agreement, this study protocol, the Clinical Trial Agreement, all applicable federal and local regulations, and any conditions of approval imposed by the reviewing IRB and/or FDA.

The Principal Investigator shall:

- Indicate acceptance of this study protocol in writing by signing the Investigator Signature page of this study protocol and any applicable amendments;
- Conduct this study in compliance with this study protocol and any applicable amendments;
- Create and maintain adequate source documentation throughout this study and make source documentation available as requested for monitoring visits or audits;
- Ensure the investigational device is used solely by authorized users at the site;
- Ensure the investigational device is used in accordance with this study protocol and product labeling;
- Refrain from implementing any modifications to this study protocol without agreement from Gala, the applicable IRB, and national regulatory authority as required;
- Promptly document and explain any deviation from the approved study protocol during the course of this study;
- Ensure the investigational site has an adequate staff, resources and training, and document delegations of duties throughout the study;
- Ensure study staff members have document study protocol training;
- Ensure adequate facilities exist and are maintained during this study;
- Ensure that maintenance and calibration of all equipment relevant to the clinical investigation is appropriately performed and documented as requested;
- Ensure the accuracy, completeness, legibility, and timeliness of all data reported to Gala (including source documentation as well as CRFs);
- Maintain accurate and complete device accountability records;
- Allow and participate monitoring and auditing activities as requested;
- Allow and participate in FDA inspection activities;
- Ensure all study-related records are retained as required; and
- Ensure accurate and timely preparation of reports required by applicable regulations.

Gala retains the right to terminate participating investigational sites for failure to comply with investigator responsibilities, or requirements imposed by applicable IRBs and the FDA.

12.4 Study Initiation

Prior to the initiation of the clinical investigation, the qualifications of the site Principal Investigator and staff, and adequacy of the clinical investigation sites shall be verified and documented. Prior to initiating patient enrollment at the investigational site, Gala

will conduct a Site Initiation Visit inclusive of training on the clinical investigation plan and operation of the device and procedure for the Principal Investigator and research staff. Study enrollment may not begin until the site receives notification that it has been activated by Gala and has received IRB approvals and completed SIV training.

12.5 Amendments to the Clinical Investigational Plan (CIP)

All amendments to the CIP will be agreed upon between the Sponsor and the clinical investigator(s) and will be recorded with a justification for the changes. The investigator is responsible for submitting all amendments of the CIP to their IRB in accordance with IRB procedures.

The study may be amended to expand the study to include additional subjects and/or longer therapy periods (i.e., > 6 months) if subjects are positively responding to the investigational therapy.

12.6 Deviations from the Clinical Investigational Plan

Protocol deviations should be avoided unless deemed necessary by the investigator to protect the life or physical well-being of a subject in an emergency. The site principal investigator shall notify the sponsor and the reviewing IRB of any deviation from the investigational plan to protect the life or physical well-being of a subject in an emergency. Such notice shall be given as soon as possible, but in no event later than 5 working days after the emergency occurred.

All deviations from the approved CIP should be documented in the study file and reported to IRB as necessary per governing IRB policy and in accordance with §812.35(a). Except in an emergency, the sponsor should be made aware if any deviation from the CIP is anticipated that may affect the scientific soundness of the CIP or the rights, safety, or welfare of human subjects

All study variances will be reviewed by the Medical Monitor and study sponsor to determine the need to amend the CIP or to terminate the investigation.

12.7 Informed Consent Process

The investigator is responsible for obtaining and documenting informed consent from each participating subject in accordance with applicable regulatory requirements and the institution's procedures for clinical research. Informed consent should adhere to GCP and to ethical principles that have their origin in the Declaration of Helsinki. Only an IRB-approved ICF for this CIP may be used to document a subject's consent.

12.8 Device Accountability

Upon receipt of investigational products from the study sponsor, the Investigator is responsible for accountability of the investigational devices in accordance with applicable regulations. A device accountability log will be used to track device receipt, use, and return/disposal of the devices.

Study device should be stored in a secure environment with access provided only to key study personnel who have the appropriate authorization. It is investigator's responsibility to ensure that the study device is used only for study subjects under PI's personal supervision or under the supervision of a properly trained sub-Investigator. Study Device Accountability Log should be updated every time a device is received at the site, used in a subject, disposed of or returned to the

sponsor. During the study, devices that are intended to be disposable (e. g. catheter) may be disposed of at the site or returned to the study sponsor if requested.

Monitors will routinely verify that investigational product documentation is accurate and complete throughout the study including at the close-out visit.

The investigator must return unused devices to the sponsor at study completion, closing of the study site, or as requested by the sponsor.

12.9 Publication Policy

Any proposed publication or presentation (including a manuscript, abstract or poster) will be published, or submitted for publication, in accordance with the terms of the Clinical Trial Agreement.

1 INTRODUCTION

This Statistical Analysis Plan (SAP) provides a description of the statistical methods and procedures to be implemented for the analyses of data collected from the CS003 study entitled ‘A Feasibility Study: A Safety Evaluation of the RheOx™ on Patients with Chronic Bronchitis in the United States’. Any deviations from this analysis plan will be substantiated by sound statistical rationale and will be documented in the final clinical study report.

All analyses described in this plan are considered a priori analyses in that they have been defined prior to lock/freeze of the database. Analyses designed after database lock or freeze are deemed post-hoc and will be considered exploratory. All post hoc analyses will be clearly identified in the clinical study report.

2 STUDY OBJECTIVES

The primary objective of this study is to assess the safety of RheOx in patients with chronic bronchitis. The secondary objective is to assess the clinical utility of RheOx in patients with chronic bronchitis.

3 STUDY OVERVIEW

3.1 Study Design

This is a prospective, single arm, feasibility study to assess the safety and clinical utility of RheOx in patients with chronic bronchitis in the United States.

Patients undergo the RheOx Bronchial Rheoplasty procedure in two bronchoscopic sessions; the first to treat the right lung (Bronchoscopy 1 / index procedure) and the second to treat the left lung (Bronchoscopy 2) approximately 4-weeks later. Study follow-up visits occur at 1-week following each treatment and at 1-month, 3-months, 6-months, 10-months, 12-months, and 2, 3, 4 and 5 years after the second treatment.

For a detailed schedule of procedures, refer to the Schedule of Events table in the study protocol.

3.2 Study Endpoints

CONFIDENTIAL:

This document and its contents are the property of Gala Therapeutics, Inc. Any use, reproduction or distribution without the written permission of Gala Therapeutics, Inc. is prohibited.

	TYPE: Clinical Trial Document	Document No:	CLN-0000X
	TITLE: CS003 Statistical Analysis Plan	Revision:	A
		Release Date:	
		DCN	Page 5 of 44

3.2.1 Safety

The primary safety analysis is the incidence of serious adverse events (SAE) of interest through 12 months defined as the following:

- Death
- COPD exacerbation, as defined as an acute worsening in respiratory symptoms requiring additional therapy, that requires a hospital stay of greater than 24 hours
- Pneumothorax within 2 days of either Gala Treatment procedure
- Pneumonia within 7 days of either Gala Treatment procedure, as defined as an increase in respiratory symptoms, fever, sputum production and or purulence with radiographic confirmation
- Respiratory Failure as defined as a requirement for mechanical ventilatory support for > 24 hours
- Arrhythmia requiring intervention or sustained (≥ 30 seconds) ventricular tachycardia

In addition to the primary safety analysis, additional pre-specified safety analyses will be performed in order to assess the totality of the safety profile of RheOx. Other, prespecified safety analyses include the incidence of treatment emergent adverse events (AE) and SAEs and an analysis of COPD exacerbations by severity.

3.2.2 Clinical Utility

The clinical utility endpoints include:

- The change from baseline at 6 and 12 months in St. George's Respiratory Questionnaire (SGRQ)
- The change from baseline at 6 and 12 months in COPD Assessment Test (CAT)
- Hospitalization rate (not including the planned bronchoscopy procedures) from discharge from the initial RheOx Bronchial Rheoplasty procedure (Visit 2) through 12 months

3.2.3 Other Endpoints

In addition, the protocol also prespecified the following exploratory measures for assessment including changes from baseline to follow-up in:

- Responder rates utilizing established clinically meaningful thresholds for SGRQ (4 points) and CAT (2 points)

CONFIDENTIAL:

This document and its contents are the property of Gala Therapeutics, Inc. Any use, reproduction or distribution without the written permission of Gala Therapeutics, Inc. is prohibited.

	TYPE: Clinical Trial Document	Document No:	CLN-0000X
	TITLE: CS003 Statistical Analysis Plan	Revision:	A
		Release Date:	
		DCN	Page 6 of 44

- Change in other QOL measures including CASA-Q and EXACT-PRO
- Change in lung function as measured by FEV₁ and FVC
- Change in sleep patterns as assessed by the Insomnia Sleep Index (ISI)
- Change in cough count as assessed by a cough counting monitor
- Mucin concentrations (MUC5AC, MUC5B) from induced sputum samples
- Quantitative High-Resolution CT Scan (HRCT) metrics including airway volume, total airway count, and lobar volumes
- Device performance.

4 STATISTICAL METHODOLOGY

4.1 Sample Size Determination

Since this is an early feasibility study, no formal sample size calculations were conducted. Up to 30 patients will be enrolled and treated with the study device to assess the effect of the investigational device in the target population. This sample size was based upon clinical judgement rather than statistical considerations.

4.2 Analysis Populations

4.2.1 Evaluable Population

The Evaluable Population will include all patients who received at least one RheOx treatment. All analyses will be based on the evaluable population.

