- Change in other QOL measures including CASA-Q and EXACT-PRO
- Change in lung function as measured by FEV₁ and FVC
- Change in sleep patterns as assessed by the Insomnia Sleep Index (ISI)
- Change in cough count as assessed by a cough counting monitor
- Mucin concentrations (MUC5AC, MUC5B) from induced sputum samples
- Quantitative High Resolution CT Scan (HRCT) metrics including airway volume, total airway count, and lobar volumes
- Device performance

In addition to the endpoints described above, additional safety analyses in support of the primary study outcome and to assess the totality of safety profile of RheOx, will be conducted.

Adverse events reported from the day of the index procedure through completion or termination of the study will be assessed. AEs and SAEs will be summarized using a standard medical coding dictionary (MedDRA). AEs and SAEs will be also analyzed by severity, relatedness to the device and/or procedure and within discrete time periods in relation to the index procedure.

COPD exacerbations will also be analyzed by severity (mild, moderate, and severe) based on commonly accepted clinical definitions as defined in GOLD 2018 Report¹⁸.

Statistical Considerations

As this is a feasibility study, endpoints will not be powered for statistical significance. Descriptive statistics will be utilized to summarize and report on data for all subject and outcome variables.

Categorical data (e.g., age, gender) will be reported in frequency distributions. Certain dichotomous data (e.g., Adverse Events) will also be presented as rates. Continuous data (e.g., age, FEV₁) will be

summarized using mean, standard deviations, medians, minimums, maximums, and interquartile ranges.

All patients that enter the procedure room for the index RheOx Bronchial Rheoplasty procedure (Visit 2) will be included in the analysis.

Additional subgroup and other multivariable analyses may be performed including examination of the association between subject risk factors (e.g., age, gender) and trial outcomes, and the potential contributions of these factors.

LIST OF ABBREVIATIONS

6MWT	Six Minute Walk Test
AE	Adverse Event
ARDS	Acute Respiratory Distress Syndrome
BAL	Bronchoalveolar lavage
CASA-Q	Cough and Sputum Assessment Questionnaire
CAT	COPD Assessment Test
CBC	Complete Blood Count
CIP	Clinical Investigational Plan
COPD	Chronic Obstructive Pulmonary Disease
CRF	Case Report Form
CT scan	Computed Tomography scan; also referred to as CAT scan

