3.2.3 Other Endpoints

Other, tertiary and exploratory endpoints will also be assessed including changes from baseline to follow-up in;

- Responder rates utilizing established clinically meaningful thresholds for SGRQ (4 points)¹⁷ and CAT (2 points)¹⁶
- Change in other QOL measures including CASA-Q and EXACT-PRO
- Change in lung function as measured by FEV₁ and FVC
- Change in sleep patterns as assessed by the Insomnia Sleep Index (ISI)
- Change in cough count as assessed by a cough counting monitor
- Mucin concentrations (MUC5AC, MUC5B) from induced sputum samples
- Quantitative High Resolution CT Scan (HRCT) metrics including airway volume, total airway count, and lobar volumes
- Device performance

In addition to the endpoints described above, additional safety analyses in support of the primary study outcome and to assess the totality of safety profile of the RheOx Bronchial Rheoplasty, will be conducted.

Adverse events reported from the day of the index procedure through completion or termination of the study will be assessed. AEs and SAEs will be summarized using a standard medical coding dictionary (MedDRA). AEs and SAEs will be also analyzed by severity, relatedness to the device and/or procedure and within discrete time periods relative to the index procedure.

COPD exacerbations will also be analyzed by severity (mild, moderate, and severe) based on commonly accepted clinical definitions as defined in GOLD 2018 Report¹⁸.

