7.2.2 Visit #2. Bronchoscopy #1 / Treatment Session #1

Eligible subjects are scheduled for the first bronchoscopy and treatment session within 90 days of completing screening procedures. Pre-operative procedures (e.g., physical exam, complete blood count) are completed in accordance with the Schedule of Events table prior to the bronchoscopy.

Note: Pre and post-bronchoscopy care (including medications) should be administered at the discretion of the treating physician per the institution's standard of care.

Upon successful completion of the preoperative procedures, the subject undergoes a bronchoscopy procedure in accordance with standard institutional protocol. Anesthesia is administered. The airways are visualized, and BAL completed. If any complications that preclude continued participation in the study are revealed, then the treatment is halted. If subject has not experienced any complications that precludes continued participation in the study, then RheOx therapy is administered to the target sites in the right lung in accordance with the instructions for use. The clinical investigator ensures FiO₂ does not exceed 40% during energy delivery. Prior to the initiation of energy delivery and during at least one energy delivery a 6 second 3 lead EKG strip is recorded. An EKG rhythm strip from anesthesia monitoring is adequate.

The subject is recovered in accordance with standard institutional procedures. The study investigator determines whether an overnight stay is clinically warranted, and the subject is discharged at the investigator's discretion. Any observed adverse events are reported accordingly.

Note: Subjects may be excluded or treatment delayed at the investigator's discretion if the patient has an active respiratory infection (e.g., common cold, pneumonia, MAI), COPD exacerbation or any other significant adverse event that may compromise the procedure.

Likewise, if at the time of the scheduled procedure the study physician determines the patient has clinical signs or findings (i.e., pulmonary nodule requiring follow-up, abnormal cardiac rhythm) that may adversely impact the

safety of the procedure, the procedure will be postponed pending treatment of the condition and reassessment of the patient.

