8.3 Evaluable Cohort

All subjects who have entered the treatment room for Visit #2 will be included in the safety endpoint analysis (Safety Population). Subjects who have received at least one treatment will be included in the evaluable cohort for clinical utility.

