Patient Meeting Criteria #3 n (%)	xx (xx.x%)	xx (xx.x%)	xx (xx.x%)	xx (xx.x%)	xx (xx.x%)	xx (xx.x%)	xx (xx.x%)
Patient Meeting Criteria #4 n (%)	xx (xx.x%)	xx (xx.x%)	xx (xx.x%)	xx (xx.x%)	xx (xx.x%)	xx (xx.x%)	xx (xx.x%)

CONFIDENTIAL:

This document and its contents are the property of Gala Therapeutics, Inc. Any use, reproduction or distribution without the written permission of Gala Therapeutics, Inc. is prohibited

	TYPE: Clinical Trial Document	Document No:	CLN-0000X
	TITLE: CS003 Statistical Analysis Plan	Revision:	A
		Release Date:	
		DCN	Page 32 of 44

Table # 14.3.1 Serious Adverse Events of Interest and Hospitalizations
Evaluable Population

	Treatment Recovery Period [1]	3 Months [2]	6 Months [3]	12 Months [4]	Total Events through 12 Months [5]
	n (%) [events]	n (%) [events]	n (%) [events]	n (%) [events]	n (%) [events]
	(N)	(N)	(N)	(N)	(N)
Death	xx (xx.x%) [xx]	xx (xx.x%) [xx]	xx (xx.x%) [xx]	xx (xx.x%) [xx]	xx (xx.x%) [xx]
COPD Exacerbation	xx (xx.x%) [xx]	xx (xx.x%) [xx]	xx (xx.x%) [xx]	xx (xx.x%) [xx]	xx (xx.x%) [xx]
Pneumothorax	xx (xx.x%) [xx]	xx (xx.x%) [xx]	xx (xx.x%) [xx]	xx (xx.x%) [xx]	xx (xx.x%) [xx]
Pneumonia	xx (xx.x%) [xx]	xx (xx.x%) [xx]	xx (xx.x%) [xx]	xx (xx.x%) [xx]	xx (xx.x%) [xx]
Respiratory Failure	xx (xx.x%) [xx]	xx (xx.x%) [xx]	xx (xx.x%) [xx]	xx (xx.x%) [xx]	xx (xx.x%) [xx]
Arrythmia	xx (xx.x%) [xx]	xx (xx.x%) [xx]	xx (xx.x%) [xx]	xx (xx.x%) [xx]	xx (xx.x%) [xx]
Total					
Hospitalizations					
n (%)	xx (xx.x%)	xx (xx.x%)	xx (xx.x%)	xx (xx.x%)	xx (xx.x%)
Rate per pt-yr (n events)	x.xx [xx]	x.xx [xx]	x.xx [xx]	x.xx [xx]	x.xx [xx]

[1] Any event occurring after Bronchial Rheoplasty 1 procedure through 30 days following Bronchial Rheoplasty 2 procedure.

[2] Follow-up period through 3 months after Bronchial Rheoplasty 2, excluding either treatment recovery period.

[3] Follow-up period between 3 months and 6 months after Bronchial Rheoplasty 2.

[4] Follow-up period between 6 months and 12 months after Bronchial Rheoplasty 2.

[5] All treatment-emergent events occurring after Bronchial Rheoplasty 1 procedure through 12 months after Bronchial Rheoplasty 2.

CONFIDENTIAL:

	TYPE: Clinical Trial Document	Document No:	CLN-0000X
	TITLE: CS003 Statistical Analysis Plan	Revision:	A
		Release Date:	
		DCN	Page 33 of 44

Table # 14.3.2 High Level Summary of Non-Serious Adverse Events
Evaluable Population

	Total Events through 12 Months[1] n (%) [events] (N)
Number of Subjects with AEs	xx (x.x%) [xx]

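### The SAP bases the primary safety incidence on treated patients only, where protocol 8.3 requires everyone who entered the Visit 2 treatment room, and gives no reason

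*SAP*

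**What the plan says.** Protocol 8.3 defines two sets. For safety: "All subjects who have entered the treatment room for Visit #2 will be included in the safety endpoint analysis (Safety Population"). For the secondary objective: "Subjects who have received at least one treatment will be included in the evaluable cohort for clinical utility". The protocol synopsis, under Statistical Considerations, also counts by room entry and does not limit this to safety: "All patients that enter the procedure room for the index RheOx Bronchial Rheoplasty procedure (Visit 2) will be included in the analysis".

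SAP 4.2 contains one set, patients with at least one RheOx treatment, and 4.2.1 adds: "All analyses will be based on the evaluable population". The SAP's list of tables gives Evaluable as the population for every safety table, 14.3.1 to 14.3.8. The SAP neither mentions the protocol's Safety Population nor explains its absence. The SAP introduction promises a rationale for deviations from the SAP, which does not cover the SAP's own departure from the protocol.

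On the order of events at Visit 2, protocol 7.2.2 puts anesthesia, airway visualization and lavage before RheOx, and then says: "If any complications that preclude continued participation in the study are revealed, then the treatment is halted".

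**The concern.** Safety is the primary objective, and the primary result is a simple proportion of patients. Under the SAP rule a patient can leave that proportion because of the kind of event it is meant to count: an event after room entry but before the first activation can prevent activation, and the patient then never joins the Evaluable Population. Protocol 8.3 avoids this by fixing membership at room entry, before the procedure can influence it. With at most 30 treated patients, one excluded event would be visible in the reported rate.

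**Working it through.** There is no stated figure to reproduce. SAP 4.1 gives no sample size calculation, and SAP 4.8 rules out inferential testing of safety. The check compares the definitions and then sizes the difference.

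**1. Definitions side by side.**

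| Source | Who is counted | For what |
|---|---|---|
| Protocol 8.3 | Entered the Visit 2 treatment room | Safety endpoint |
| Protocol 8.3 | At least one treatment | Clinical utility |
| Protocol synopsis | Entered the procedure room for the index procedure | The analysis, unspecified |
| SAP 4.2.1 | At least one treatment | All analyses |

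No protocol statement of an analysis population supports treated-only safety. The sets differ by the patients who entered the room and were never activated.

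**2. Can such a patient have a qualifying event?** Of the six components in protocol 3.2.1 and SAP 3.2.1, four do not require a treatment date: death, COPD exacerbation with a stay over 24 hours, mechanical ventilation over 24 hours, and arrhythmia meeting the stated criteria. Protocol 10.2 lists respiratory failure and death among foreseeable anesthesia complications, and abnormal cardiac rhythm among foreseeable events. The other two, pneumothorax within 2 days and pneumonia within 7 days, are tied to a Gala Treatment procedure, which a never-activated patient has not had.

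**3. Size.** Let n be the number treated and x those among them with an event. The SAP rate is x/n. Add one never-activated entrant:

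- with an event, the protocol rate is (x+1)/(n+1), a rise of (n − x)/[n(n+1)];
- without an event, it is x/(n+1), a fall of x/[n(n+1)].

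The maximum n = 30 is from SAP 4.1. The values of x, the single entrant and n = 20 are assumptions. Intervals are exact (Clopper-Pearson) 95%.

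| SAP rule | Protocol rule | Change (points) |
|---|---|---|
| 0/30 = 0% (0 to 11.6) | 1/31 = 3.2% (0.1 to 16.7), with event | 30/930 = +3.2 |
| 3/30 = 10.0% (2.1 to 26.5) | 4/31 = 12.9% (3.6 to 29.8), with event | 27/930 = +2.9 |
| 3/30 = 10.0% (2.1 to 26.5) | 3/31 = 9.7% (2.0 to 25.8), no event | 3/930 = −0.3 |
| 0/20 = 0% (0 to 16.8) | 1/21 = 4.8% (0.1 to 23.8), with event | 20/420 = +4.8 |
| 2/20 = 10.0% (1.2 to 31.7) | 2/21 = 9.5% (1.2 to 30.4), no event | 2/420 = −0.5 |

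These rows are examples, not bounds. Fewer treated patients or more entrants enlarge the change: 0/10 against 1/11 is 9.1 points. A higher event rate enlarges the fall from an event-free entrant: 9/30 against 9/31 is 1.0 point. With no never-activated entrant the change is zero.

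**4. Start of the safety period.** SAP 4.8 counts events during or after bronchoscopy #1, and SAP 4.8.1 runs the primary analysis from bronchoscopy #1. Protocol 3.2.3 agrees: "Adverse events reported from the day of the index procedure through completion or termination of the study will be assessed". The footnotes of Table 14.3.1 are looser. Footnote [1] reads "Any event occurring after Bronchial Rheoplasty 1 procedure through 30 days following Bronchial Rheoplasty 2 procedure" and footnote [5] reads "All treatment-emergent events occurring after Bronchial Rheoplasty 1 procedure through 12 months after Bronchial Rheoplasty 2". Read literally, *after* omits the procedure itself, and a never-activated patient has no Bronchial Rheoplasty 1 at all.

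**The case against.** The best defence is that the note in protocol 7.0 ties enrollment to the first activation, and SAP Table 14.1.1 accordingly equates enrolled with treated. That may be where the SAP's choice came from, but the SAP does not say so. Protocol 8.3 defines the safety set by room entry rather than enrollment, and protocol 7.1 places enrollment before both bronchoscopies.

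Second, such a patient would not vanish. SAP 4.8.2 lists all adverse events, SAP 4.3 lists reasons for exclusion from populations, and Table 14.1.2 counts Bronchoscopy 1 not completed among all patients. This gives partial visibility, but none of it returns the patient to the primary incidence.

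Third, the study is unpowered and descriptive, the intervals above overlap widely, and there may be no such patient. All of that stands, and it limits the consequence.

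Three stronger readings are tempting and not supported:

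- A reader might infer that the primary analysis loses events on the procedure day. SAP 4.8 and 4.8.1 both start at bronchoscopy #1, SAP 3.1 identifies that session with the index procedure, and footnote [5] uses the term treatment-emergent, which SAP 4.8 defines as including the procedure. Only the footnote wording is at fault.
- A reader might worry about a patient halted at one session and activated at a later one. The notes to protocol 7.2.2 allow a procedure to be delayed or postponed, but the documents do not describe repeating a halted bronchoscopy.
- A reader might infer that the 2-day and 7-day windows should simply run from an untreated bronchoscopy. Protocol 3.2.1 ties them to a Gala Treatment procedure, so this would change the primary endpoint definition. Protocol 8.3 does not require it.

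**Conclusion.** SAP 4.2.1 is wrong as written against protocol 8.3: it narrows the population of the primary safety endpoint without a reason, in a way that can exclude a patient because of a qualifying event. It should be fixed.

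The effect depends on how many entrants were never activated, which the documents do not give. One with an event makes the SAP rate too low, by about 3 percentage points at 30 treated when the treated rate is 0 to 10%. One without an event makes it too high, by at most 0.3 points over the same range. It cannot be said from the documents that the reported rate is in fact biased. Patient oversight is not weakened either: the stopping rules (protocol 7.6.1), the interim safety review (7.6.2) and 24-hour SAE reporting (10.1.2) do not use the SAP population.

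**What to change.** 1. Add the protocol 8.3 Safety Population to SAP 4.2 and use it for SAP 4.8 and the safety rows of Tables 14.3.1 to 14.3.8. If a treated-only result is also wanted, state the reason and show it beside the protocol set.
2. Keep Evaluable for clinical utility. This includes the hospitalization rows of Table 14.3.1, since SAP 3.2.2 classes hospitalization as clinical utility. That table then has two denominators, so its shell needs a separate N for those rows.
3. Report in Table 14.1.1 the number who entered the room but were not treated, with reasons. If it is zero, the table shows that the two sets coincide.
4. Reword the safety table footnotes that start after Bronchial Rheoplasty 1 so that they include the day of bronchoscopy #1, as SAP 4.8 and 4.8.1 do.

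How the 2-day and 7-day windows apply to an untreated bronchoscopy is a separate point for the sponsor to reconcile with protocol 3.2.1.

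The cost is a short SAP revision and a little programming. Events around the procedure should already be recorded (protocol Table 7.1, Note 2). Twelve-month data for never-activated entrants may be incomplete: the subject identifier is assigned at enrollment (protocol 9.2), and the fallback follow-up rule in protocol 7.4 covers only a missed Bronchoscopy #2. The follow-up available should be reported with the result. The reported SAE rate may become less favourable.
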